4.1 Conventions

4.1.1 Baseline definition

Assessments performed at or shortly before the screening visit are considered as baseline. If more than one measurement of the same item satisfies this condition, the most recent measurement is considered as baseline. Collection of PBAC assessment was not included in protocol version V01. For subjects starting with protocol version V01, the first assessment under protocol version V02 serves as baseline.

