1.2 Secondary objective

The secondary objectives of this study are to:

- Assess the quality of life (QoL) of VWD patients undergoing on-demand treatment with a VCP
- Assess the safety of the VCP used for on-demand VWD treatment

The following objectives are also pursued except for Croatian centers:

- Determine the effectiveness of the VCP used in the treatment of bleeding episodes (BEs)
- Determine the effectiveness of the VCP used in surgical prophylaxis
- Assess the patients' joint status using the Hemophilia Joint Health Score (HJHS)
- Assess the menstrual bleeding intensity of female patients of child-bearing potential

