4.7.2 Secondary Endpoints

Secondary endpoints are:

- Spontaneous annualized bleeding rate (SABR), calculated in analogy with TABR
- Data on the consumption of VCP product (VWF/FVIII IU/kg per month per patient) used for routine on-demand treatment

The following secondary efficacy endpoints will be studied except in Croatian centers:

- Effectiveness of VCP in the treatment of BEs based on the proportion of successfully treated BEs (definition see section 6.2)
- Effectiveness of surgical prophylaxis with VCP based on the proportion of successfully treated surgeries (definition see section 6.3)
- Pictorial Blood Loss Assessment Chart (PBAC) score

Regarding the VCP administration data, the following parameters will be documented:

- Dates and times of VCP injections
- Doses of VCP in IU and IU/kg and VCP batch numbers
- Reason for VCP injection (prophylaxis, treatment of BE, surgery)

Statistical Analysis Plan	Version 3.0		Page 12 of 17
Sponsor	Octapharma	Protocol No	WIL-29

Descriptive statistics will also be presented for the SABR and for time in study, exposure days, number of infusions and dosages of VCP overall and by reason for VCP injection.

Additionally, descriptive statistics will be presented for the traumatic annualized bleeding rate (TRABR), calculated in analogy with TABR.

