4.7.4 Menstrual Bleedings (only female patients of childbearing potential)

For female patients, the results of the PBAC score over time will be summarized in descriptive tables for each complete menstrual cycle including changes to baseline.

Annualized rates of heavy menstrual bleedings will be calculated in analogy with TABR and summarized in descriptive tables. For the exploratory endpoint 'Annualized rate of heavy menstrual bleeds' descriptive statistics will be tabulated.

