6 DERIVATIONS AND TRANSFORMATIONS

6.1 Formulas for derived variables

Variable	Description
Durations between two dates	Later date minus earlier date plus 1, expressed in days. (Remark: Duration will be 1, if both dates are the same.)
Surgery Period	(Date of surgery – date of last VCP treatment for surgery + 1)/365.25
Total Annualized Bleeding Rate (TABR)	Number of bleedings excluding menstrual bleedings / (date of study completion – date of screening + 1)/365.25 (Surgery periods, and BEs occurring within these surgery periods, will be excluded from the calculation of TABR. BEs occurring at day of surgery but prior to start of surgery/start of treatment for surgery will be included into calculation)
Spontaneous Annualized Bleeding Rate (SABR)	Number of spontaneous bleedings / (date of study completion – date of screening + 1)/365.25 (Surgery periods, and BEs occurring within these surgery periods, will be excluded from the calculation of SABR. BEs occurring at day of surgery but prior to start of surgery/start of treatment for surgery will be included into calculation)
Traumatic Annualized Bleeding Rate (TRABR)	Number of spontaneous bleedings / (date of study completion – date of screening + 1)/365.25 (Surgery periods, and BEs occurring within these surgery periods, will be excluded from the calculation of TRABR. BEs occurring at day of surgery but prior to start of surgery/start of treatment for surgery will be included into calculation)
Heavy Menstrual Bleeding Rate (HMBR)	Number of heavy menstrual bleedings* / (date of study completion – date of screening + 1)/365.25 (* for a definition refer to section 6.4)
ED	Exposure day = each calendar day the subject received VCP

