6.4 Criteria for Heavy Menstrual Bleeding

Any menstrual bleeding that meets any of the following criteria will be classified as Heavy Menstrual Bleeding for analysis purposes:

- Interferes with daily activities such as work, housework, exercise, or social activities,
- Requires changing pads/tampons more frequently than hourly (referred to as 'flooding'),
- Lasts 7 or more days,
- Includes the presence of cloths > 1 cm combined with a history of flooding,
- PBAC score ≥ 185 , whenever PBAC score are applicable.

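### The heavy-menstrual-bleeding rate pools time with and without PBAC collection, so it mixes two case definitions and may be biased low

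*SAP*

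**What the plan says.** - **Formula.** SAP 6.1 defines HMBR as "Number of heavy menstrual bleedings* / (date of study completion – date of screening + 1)/365.25". The row makes no allowance for protocol version or country.
- **Case definition.** SAP 6.4 classes a menstrual bleed as heavy on any one of five criteria. Four need no PBAC: interference with everyday activity, flooding, a duration of a week or more, and clots together with past flooding. The fifth is a PBAC score of at least 185, "whenever PBAC score are applicable".
- **PBAC by protocol version.** SAP 4.1.1 says "Collection of PBAC assessment was not included in protocol version V01". It adapts the PBAC baseline for the affected patients: "For subjects starting with protocol version V01, the first assessment under protocol version V02 serves as baseline".
- **PBAC by country.** SAP 4.7.2 introduces the list containing the PBAC score with "The following secondary efficacy endpoints will be studied except in Croatian centers". SAP 1.2 introduces the list containing menstrual bleeding intensity with "The following objectives are also pursued except for Croatian centers".
- **Analysis text.** SAP 4.7.4 says "Annualized rates of heavy menstrual bleedings will be calculated in analogy with TABR". It restricts neither version nor country and calls the rate exploratory. SAP 4.1.3 pools all countries and centres in the tables.
- **Documented time.** SAP 4.1.2 bases annualised bleeding rates on documented time, without saying what counts as documented for menstrual data.
- **Surgery.** The TABR, SABR and TRABR rows of SAP 6.1 each exclude surgery periods. The HMBR row does not.

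**The concern.** An annualised rate is sound only if an event could be detected, under one definition, throughout the time in its denominator. Here a bleed that is heavy by PBAC alone cannot be counted under V01 or where PBAC is not studied, yet that time still enters the denominator. The SAP recognised the V01 gap when it set the PBAC baseline but did not carry it through to HMBR.

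TABR leaves menstrual bleeds out, so HMBR is the only annualised rate the plan gives for them. Protocol Table 4 classes heavy menstrual bleeding as major. Protocol 6.2 intends the data for historical comparison with a prophylaxis study. A rate whose case definition shifts with protocol version and country is a weak reference for that purpose.

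**Working it through.** The documents give no figure for HMBR, so there is nothing to reproduce first. I read the 6.1 row as bleeds divided by (days / 365.25).

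**Inputs**
- u: share of woman-time without PBAC. Not given; assumed.
- p: share of heavy bleeds meeting only the PBAC criterion. Not given; assumed.
- Follow-up of about 6 months (Protocol 8.4.2); 183 days in the example.

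**Step 1: general form.** Assume an even bleed rate, the same p throughout, and the other four criteria captured at all times. A heavy bleed is lost only if it falls in PBAC-free time and qualifies by PBAC alone:

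reported / true = 1 − u × p

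| u | p = 0 | p = 0.10 | p = 0.25 | p = 0.50 | p = 1 |
|---|---|---|---|---|---|
| 0 | 1.00 | 1.00 | 1.00 | 1.00 | 1.00 |
| 0.10 | 1.00 | 0.99 | 0.975 | 0.95 | 0.90 |
| 0.25 | 1.00 | 0.975 | 0.938 | 0.875 | 0.75 |
| 0.50 | 1.00 | 0.95 | 0.875 | 0.75 | 0.50 |

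No cell exceeds 1.

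**Step 2: one woman.** Take 183 days and six heavy bleeds, with three of them in the first 92 days, before PBAC.
- True rate: 6 / (183/365.25) = 11.98 per year.
- SAP formula, p = 0: 6 bleeds counted, 11.98.
- SAP formula, p = 1/3: 3 + 3 × 2/3 = 5 counted, 9.98.
- SAP formula, p = 1: 3 counted, 5.99.
- Numerator and denominator both restricted to the 91 days with PBAC: 3 / (91/365.25) = 12.04.
- Only the denominator cut to 91 days: 24.08 (p = 0) or 20.07 (p = 1/3), a gross over-count.
- Four criteria over all time, p = 1/3: 6 × 2/3 = 4 counted, 4 / (183/365.25) = 7.98. This is a narrower definition and so a lower level, but the same one throughout.

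**Step 3: Croatian centres.** Let c be their share of woman-time (not given) and let u now be the PBAC-free share elsewhere. Take c = 0.10, u = 0.25 and p = 0.25 for illustration.
- Croatian time counted, four criteria recorded there: 1 − (0.10 + 0.25) × 0.25 = 0.9125.
- Croatian time counted, no menstrual intensity recorded there: 1 − 0.10 − 0.25 × 0.25 = 0.8375.
- Croatian women left out of both parts: 1 − (0.25/0.90) × 0.25 = 0.931.

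**Step 4: surgery periods.** Section 4.7.4 calls for analogy with TABR, which implies excluding surgery time and the bleeds within it. The 6.1 row says nothing. The documents give no surgery time for these women, so neither the size nor the direction of the effect can be stated.

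**The case against.** The strongest reply is that four of the five criteria work without PBAC. Only a bleed that reaches 185 and meets none of the others is lost, and such bleeds may be rare. SAP 6.4 plainly foresees missing scores. SAP 4.1.2 limits rates to documented time. Croatian women may already fall outside the menstrual analysis, since SAP 1.2 drops that objective there, and they would then add neither bleeds nor time. The endpoint is exploratory, and SAP 4.7.4 also summarises the PBAC score by cycle.

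Much of this stands. It removes any certainty of an under-count and puts the lower bound at zero. It does not close the point:
- The applicability wording in 6.4 accepts that the definition varies between patients. It neither adjusts the denominator nor separates the results.
- SAP 4.1.2 does not say whether documented means by diary or by PBAC, while the 6.1 formula runs on visit dates. A programmer following 6.1 would include all V01 and Croatian time.
- The four other criteria may be less well captured than they look. Among the diary items in Protocol 8.5.3, start and end times give duration. Interference, flooding and clots have no field of their own and can enter only through the minor/major severity rating.

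A reader might infer that HMBR is certainly too low, or that Croatian women are counted as free of heavy bleeds. The documents support neither. The shares are unknown, the V01 text is not supplied, and the current protocol has menstrual bleeds recorded with a severity rating. Nor is restricting the main rate to PBAC time a clear improvement: it discards heavy bleeds validly found by the other criteria and shortens windows that are only about 6 months long.

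**Conclusion.** The point holds as a possible bias of known direction and unknown size. As written, HMBR pools a five-criterion and a four-criterion definition over one denominator. Missing PBAC can only lower the rate or leave it unchanged. The proportional shortfall is u × p: nil if either share is nil, 6.25% if both are 25%, and 25% if both are 50%. These percentages are assumptions, not estimates, and rest on an even bleed rate and full capture of the other criteria.

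If Croatian centres recorded no menstrual intensity but their time is counted, their whole share of woman-time is added to the shortfall. The documents leave that open. The surgery-period omission is a separate inconsistency within the SAP and is not evidence of an under-count. TABR, the primary endpoint, is unaffected. This is a worthwhile improvement rather than a serious flaw.

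**What to change.** 1. In SAP 6.1 and 4.7.4, state that centres where menstrual intensity is not assessed contribute neither bleeds nor time to HMBR.
2. Beside the five-criterion rate, report HMBR on the four non-PBAC criteria over all documented menstrual diary time, and define that time. As a sensitivity analysis, report the five-criterion rate with numerator and denominator both restricted to PBAC-collection time. Give the start date of that time for each patient and a rule for a cycle that spans the protocol switch. The two parts must be cut together.
3. Reconcile the HMBR row with 4.7.4 on surgery periods.

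The cost is some SAP wording and one or two table rows for an exploratory endpoint. The PBAC-only analysis will rest on shorter, less stable patient windows, which is why it belongs as a sensitivity analysis.

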4.1.2 Missing data

No imputations for missing data will be performed. Calculations pertaining to the derivation of annualized bleeding rates will be based on documented time periods only.

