### **8.2 STUDY ENDPOINTS**

#### **8.2.1 Primary Endpoint**

The primary endpoint of this NIS is to characterise the total annualised bleeding rate (TABR) of patients with type 3, type 2 (except 2N), or severe type 1 VWD undergoing routine on-demand treatment with a VWF-containing product.

The TABR will be calculated as the total number of spontaneous, traumatic and other BEs in the time period between the start of data collection for each patient and the Study Completion Visit, divided by the duration (in years) between the start of data collection and the Study Completion Visit. Surgery periods, and BEs occurring within these surgery periods, as well as menstrual bleeds will be excluded from the calculation of TABR.

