3.1 Full Analysis Set

The **full analysis (FAS) set** defined according to the intention-to-treat (ITT) principle will include all enrolled subjects.

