4.7.1 Primary Endpoint

Primary endpoint of this study is to estimate the total annualized bleeding rate (TABR) during on-demand treatment with any VCP.

TABR will be calculated as the total number of spontaneous bleeds, traumatic bleeds and other bleeds in the time period between screening visit and the study completion visit, divided by the duration (in years) between first dose of VCP and the study completion visit. Surgery periods, and BEs occurring within these surgery periods, will be excluded from the calculation of TABR. Menstrual bleeds will not be included in this calculation, but reported and analyzed separately.

Descriptive statistics for TABR along with exploratory 95% Confidence Intervals will be presented.

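### SAP 4.1.2 restricts bleeding rates to documented time, but the 6.1 formulas have no term for undocumented time and no end date for patients who leave early

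*SAP*

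**What the plan says.** SAP 4.1.2 gives two rules for missing data: "No imputations for missing data will be performed", and "Calculations pertaining to the derivation of annualized bleeding rates will be based on documented time periods only". It does not say what makes a period documented or how a gap is recognised.

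SAP 6.1 gives the TABR formula as "Number of bleedings excluding menstrual bleedings / (date of study completion – date of screening + 1)/365.25". I read this as a count divided by days converted to years. The SABR, TRABR and HMBR rows use the same span. A note removes surgery time: "Surgery periods, and BEs occurring within these surgery periods, will be excluded from the calculation of TABR". SABR and TRABR carry the same note. The HMBR row does not, although SAP 4.7.4 says that rate follows TABR by analogy.

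Two other passages define the TABR denominator, each with a different start:
- SAP 4.7.1: "divided by the duration (in years) between first dose of VCP and the study completion visit"
- Protocol 8.2.1: "divided by the duration (in years) between the start of data collection and the Study Completion Visit"

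Neither has a term for undocumented time. All three definitions end at study completion or the completion visit, and none gives an end date for a patient who leaves before it. The full analysis set "will include all enrolled subjects" (SAP 3.1), and SAP 4.2 expects some patients to discontinue.

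**The concern.** The primary endpoint is a count over time at risk, and the SAP describes that time in two ways. A programmer who follows 6.1 ignores 4.1.2. One who follows 4.1.2 has no formula for it.

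The difference has a direction. A stretch for which no bleeding information was obtained stays in the 6.1 denominator. If its bleeds are never recovered it adds nothing to the numerator, so it is counted as bleed-free. Protocol 8.5.3 asks for untreated bleeds as well, and a bleed managed at home may leave no medical record.

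The study exists to supply an on-demand reference for a historical comparison with a prophylaxis study (protocol 6.2). An understated rate would carry into that comparison, and a larger sample would not remove it.

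**Working it through.** **Inputs from the documents.** N = 55, SD at most 3, large-sample z, stated half-width 0.8 (SAP 1.4, protocol 8.8). Follow-up about 6 months (protocol 8.4.2), taken as D = 183 days or T = 0.5 year. Bleeds come from diaries and medical records (protocol 8.6). Physicians contact patients about missing diary information (protocol 8.9).

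**Assumed, because the documents do not give them.** True rate λ of 5, 10 or 20 per year; gap fraction f of 5%, 10% or 20%; share r of gap bleeds recovered, from 0 to 1. The one pointer to a rate is in protocol 8.5.2, which prefers at least 5 treated spontaneous bleeds in the 3 months before screening: 5 × 4 = 20 per year.

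**Step 1, the plan's own figure.** 1.96 × 3 / √55 = 0.793, which rounds to the stated 0.8.

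**Step 2, effect of a gap under 6.1.** With a gap of g = f × D days, the expected 6.1 rate is λ × [(D − g) + r × g] / D, so the bias is −λ × f × (1 − r). With zero recovery (r = 0) the bias per year is:

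| Gap fraction | λ = 5 | λ = 10 | λ = 20 |
|---|---|---|---|
| 5% | −0.25 | −0.5 | −1.0 |
| 10% | −0.5 | −1.0 | −2.0 |
| 20% | −1.0 | −2.0 | −4.0 |

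**Step 3, effect of recovery.** Take λ = 10 and a 30-day gap, so f = 30/183 = 16.4%. The 6.1 rate is 8.36 with no gap bleeds recovered, 9.18 with half and 10.0 with all. With all of them recovered, removing the 30 days but keeping their bleeds gives 10 × 183/153 = 11.96, which is too high. Numerator and denominator must therefore be cut together.

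**Step 4, comparison with precision.** The stated 0.8 needs an SD of 3 or less. Poisson variation alone gives an annualised SD of √(λ/T):
- λ = 5: √(5/0.5) = 3.16, half-width 1.96 × 3.16/√55 = 0.84
- λ = 10: √(10/0.5) = 4.47, half-width 1.18
- λ = 20: √(20/0.5) = 6.32, half-width 1.67

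An SD of 3 under Poisson implies λ of at most 9 × 0.5 = 4.5 per year, where a 10% gap costs at most 0.45. Like for like, the zero-recovery loss from a 10% gap is below the half-width at 5 and 10 per year (0.5 against 0.84; 1.0 against 1.18) and above it at 20 (2.0 against 1.67). Variation between patients would widen these intervals further.

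**Step 5, patients who discontinue.** They belong to the full analysis set. The 6.1 denominator needs a study completion date, and nothing is imputed. Unless that date is taken to mean the end of observation, which the SAP does not say, their rate is undefined.

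**The case against.** The best defence is that 4.1.2 qualifies 6.1 and does not contradict it. Surgery time is also removed by a note and not by the printed expression, so documented time could be handled the same way, including for patients who leave early. That reading is possible. But the surgery note says what is removed and defines the period; for documented time the SAP does neither.

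The protocol also limits the problem. Medical records are a second source, the physician must chase missing diary information, and exclusion criterion 11 removes patients who cannot keep a diary. This stands, and it makes the gap fraction an upper limit on the loss. A reader might infer that TABR always falls by the share of undocumented days; that is true only if none of the gap bleeds is recovered. A reader might also set a loss of 1.0 at 10 per year against the stated ±0.8 and conclude that bias exceeds precision. The ±0.8 does not apply at that rate (step 4).

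The third objection concerns the remedy, and it is right. The diary described in protocol 8.4.5 and 8.5.3 records events, and no daily entry for a bleed-free day is required. Counting only days with an entry, or ending follow-up at the last entry, could reduce time at risk to bleed dates. A patient with one bleed on day 30 who leaves on day 150 has a rate of 365.25/150 = 2.4 per year; ending at the last entry gives 365.25/30 = 12.2. Documented time must therefore mean covered time.

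**Conclusion.** The point holds as an unresolved conflict in the definition of the primary endpoint. SAP 4.1.2 sets a rule that 6.1 does not implement, 4.7.1 starts the clock elsewhere, and no end of observation is given for patients without a completion visit.

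Its numerical effect is conditional: between zero (all gap bleeds recovered) and the gap fraction times the true rate (none recovered). For a 10% gap the upper end is 0.5 to 2.0 bleeds per year over assumed rates of 5 to 20. Both the gap and the rates are assumptions, so the documents do not show that a material bias will occur.

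Nor do they say that discontinued patients will be dropped. A reader might infer it from the literal formula, but the documents support only that the denominator for these patients is undefined. The change should be made, because it is cheap and carries out the SAP's own rule.

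**What to change.** Amend SAP 6.1 and bring 4.7.1 into line in the same edit:

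- **Documented time.** Define it as the part of the interval from screening to end of observation that is covered by collected and reviewed diary pages, or confirmed retrospectively with the patient under protocol 8.9. Days without an entry inside a covered period count as bleed-free.
- **Denominators.** For TABR, SABR and TRABR use (documented days − surgery-period days falling within them)/365.25. For HMBR use documented days/365.25, unless surgery removal is also stated there.
- **Numerators.** Exclude bleeds that fall in subtracted time.
- **Discontinued patients.** End observation at the last visit or contact at which bleeding information was collected, not at the last diary entry.
- **SAP 4.7.1.** Replace the start at first VCP dose, so that the primary endpoint has one denominator.
- **Reporting.** Give documented days per patient, so that readers can see how much time was lost.

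The cost is SAP wording, one extra derived variable and slightly less person-time for patients with gaps.

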4.1.3 Pooling of centers

All tables will be presented in total over all participating countries and centers. The distribution of number of subjects per country and center will be presented in the disposition section of the report.

4.2 Demographic and other background data

The disposition of subjects (cf. Section 3) will be tabulated for the entire population. Details on important protocol deviations will be listed.

Discontinued subjects will be described by frequency distributions including the reasons and in individual listings.

Demographic data (age, weight, height, BMI, ethnic group) will be summarized in tables and presented for the FAS population. Other baseline and background data as listed below will also be analyzed by descriptive tables (according to their type /continuous/categorical) for the FAS population:

- AB0 blood group (if available)
- Age at first treatment with VCP
- Family history of VWD
- History of VWD or FVIII inhibitors
- Available historical data on VWF activity obtained by VWF:RCo, VWF:Gp1bM, VWF:Gp1bR assays, or any other method and VWF:Ag as well as VWF multimer pattern for VWD type 2A, genotype for VWD type 2B, VWF multimer pattern for VWD type 2A, and genotype for VWD type 2B
- Historical annual bleeding rate (ABR) calculated from number of bleeding episodes in the previous 6 months

Statistical Analysis Plan	Version 3.0		Page 10 of 17
Sponsor	Octapharma	Protocol No	WIL-29

- Hemophilia Joint Health Score (HJHS) at baseline
- QoL scales (PROMIS-29, SF-36; SF-10 for patients <16 years of age) at baseline
- Historical PBAC score

